7.1.4 Follow-up visit

Follow-up visits will take place as specified in APPENDIX II.

During the 3 days following their release from the hospital, subjects will be monitored by the nurses in the health areas and/or by the community agents of the different localities for potential adverse events. If an AE is observed, the latter need to inform the medical team in charge of the study for the necessary follow up.

At day 8 (+/- 1 day), urine samples will be collected for the POC-CCA test. If an AE related to liver function occurs before hospital discharge (within 24 hours after dosing), the subject will be further monitored by the study team in the villages and an additional blood sample will be collected at Day 8 for biochemistry evaluation.

At the End of Study visit (between day 14 and 21), subjects will be asked to provide stool and urine samples for Kato-Katz method and POC-CCA test. The following tests and information gathering will be also performed:

Vital signs in supine position including:

- Blood pressure (systolic and diastolic) to be assessed at least 5 minutes after resting
- Pulse rate to be assessed at least 5 minutes after resting
- Body temperature

Complete physical examination

If a subject withdraws prematurely from the trial, every effort will be made to undertake a final examination visit as soon as possible and perform all procedures of the End of Study visit.

Any ongoing medically relevant abnormal findings at the End of Study visit, including safety laboratory tests, will be followed up until resolution or stabilization (according to Section 7.4.1.6)

7.2 Demographic and Other Baseline Characteristics

At screening, the following demographic data will be collected: date of birth, date of informed consent signature, gender and height.

Medical history within the last year, consisting of all previous diseases as considered relevant by the Investigator and all hospital stays, will be recorded.

Previous medication consisting of all previous medications within the last 6 months as considered relevant by the Investigator and all regularly taken medications within the last 6 months will be recorded.

Use of caffeine or xanthine-containing beverages and concomitant medication will be assessed at screening.

7.3 Efficacy Assessments

7.3.1 Assessment of primary efficacy endpoint

Egg counts in the stools (expressed as egg count per gram of stool (epg) 14-21 days after treatment as determined by Kato-Katz method. Two stool samples will be collected from each subject on different days within a maximum of 5 days, at screening and 14-21 days after treatment. Three Kato-Katz thick smears will be prepared from each stool sample and read under the microscope.

7.3.2 Assessment of secondary efficacy endpoints

Frequency of POC-CCA test scores using the commercially available POC-CCA cassette.

7.4 Safety Assessments

The safety profile of the IMP will be assessed through the recording, reporting and analysis of baseline medical conditions, adverse events (AEs), physical examination findings including vital signs and laboratory tests.

Comprehensive assessment of any apparent toxicity experienced by each subject will be performed from the time of giving informed consent and throughout the trial. The Investigator will report any AEs, whether observed by the Investigator or reported by the subject (see Section 7.4.1.2). The reporting period for AEs is described in Section 7.4.1.3.

7.4.1 Adverse Events

7.4.1.1 Adverse Event Definitions

Adverse Event

An AE is any untoward medical occurrence in a subject or clinical investigation subject administered a pharmaceutical product, regardless of causal relationship with this treatment. An AE can therefore be any unfavourable and unintended sign (including an abnormal laboratory finding), symptom, or disease temporally associated with the use of a medicinal product, whether or not considered related to the medicinal product.

For surgical or diagnostic procedures, the condition/illness leading to such a procedure is considered as the AE rather than the procedure itself.

The Investigator is required to grade the severity or toxicity of each AE.

Investigators must assess the severity of AEs according to the Qualitative Toxicity Scale, as follows:

Mild: The subject is aware of the event or symptom, but the event or symptom is easily

tolerated.

Moderate: The subject experiences sufficient discomfort to interfere with or reduce his or her

usual level of activity.

Severe: Significant impairment of functioning: the subject is unable to carry out his or her

usual activities.

Expected side effects for the different research products are detailed in the investigator's brochure and in the informed consent.

Investigators must also systematically assess the causal relationship of AEs to IMP(s)/study treatment (including any other non-IMPs, radiation therapy, etc.) using the following definitions. Decisive factors for the assessment of causal relationship of an AE to the IMP include, but may not be limited to, temporal relationship between the AE and the IMP, known side effects of IMP, medical history, concomitant medication, course of the underlying disease, trial procedures.

Unrelated: Not reasonably related to the IMP/study treatment. AE could not medically

(pharmacologically/clinically) be attributed to the IMP/study treatment under study in this clinical trial protocol. A reasonable alternative explanation must be

available.

Related: Reasonably related to the IMP/study treatment. AE could medically

(pharmacologically/clinically) be attributed to the IMP/study treatment under study

in this clinical trial protocol.

Abnormal Laboratory Findings and Other Abnormal Investigational Findings

Abnormal laboratory findings and other abnormal investigational findings (e.g., on an ECG trace) should not be reported as AEs unless they are associated with clinical signs and symptoms, lead to treatment discontinuation or are considered otherwise medically important by the Investigator. If a laboratory abnormality fulfils these criteria, the identified medical condition (e.g., anaemia, increased ALT) must be reported as the AE rather than the abnormal value itself.

Serious Adverse Events

An SAE is any untoward medical occurrence that at any dose:

Results in death

Is life-threatening. (Note: The term "life-threatening" refers to an event in which the subject is at risk of death at the time of the event, not an event that hypothetically might have caused death if it was more severe.)

Requires inpatient hospitalization or prolongs an existing hospitalization

Results in persistent or significant disability or incapacity

Is a congenital anomaly or birth defect

Is otherwise considered to be medically important

Note: Important medical events that may not result in death, be life-threatening, or require hospitalization may be considered as SAEs when, based upon appropriate medical judgment, they may jeopardize the subject or may require medical or surgical intervention to prevent one of the outcomes listed above. Examples of such events include allergic bronchospasm requiring intensive treatment in an emergency room or at home, blood dyscrasias or convulsions that do not result in inpatient hospitalization, or the development of drug dependency or drug abuse.

For the purposes of reporting, any suspected transmission of an infectious agent via an IMP is also considered an SAE, as described in Section 7.4.1.4.

Events that Do Not Meet the Definition of an SAE

Elective hospitalizations to administer, or to simplify trial treatment or trial procedures (e.g., an overnight stay to facilitate chemotherapy and related hydration therapy application) are not considered SAEs. However, all events leading to unplanned hospitalizations or unplanned prolongation of an elective hospitalization (e.g., undesirable effects of any administered treatment) must be documented and reported as SAEs.

Events Not to Be Considered as AEs/SAEs

Medical conditions present at the initial trial visit that do not worsen in severity or frequency during the trial are defined as Baseline Medical Conditions and are not to be considered AEs. However, if adverse signs or symptoms occur in association with disease progression then these should be recorded as AEs.

Pre-defined Adverse Events of Special Interest for Safety Monitoring

Healthy subjects might experience diarrhoea, nausea, vomiting, headache, dizziness, inflammation and abdominal pain. These symptoms are almost always transient and occur early during therapy initiation and spontaneously resolve in most cases. If any of these AEs are observed, their severity should be defined based on clinical judgment of the Investigator and defined according to the Qualitative Toxicity Scale as described above.

7.4.1.2 Methods of Recording and Assessing Adverse Events

From screening visit to end of study, the subject and the parents/representatives will be queried on changes in his or her condition. During the reporting period, any unfavourable changes in the subject's condition will be recorded as AEs, whether reported by the subject or observed by the Investigator.

Complete, accurate and consistent data on all AEs experienced for the duration of the reporting period (defined below) will be reported on an ongoing basis in the appropriate section of the CRF. All SAEs must be additionally documented and reported using the appropriate Serious Adverse Event Report Form as described in Section 7.4.1.4.

It is important that each AE report include a description of the event, its duration (onset and resolution dates and times), its severity, its causal relationship with the trial treatment, any other potential causal factors, any treatment given or other action taken, including dose modification or discontinuation of the IMP, and its outcome. In addition, serious cases should be identified and the appropriate seriousness criteria documented.

Specific guidance can be found in the CRF Completion and Monitoring Conventions provided by the Sponsor.

7.4.1.3 Definition of the Adverse Event Reporting Period

The AE reporting period for safety surveillance begins at screening visit, (date of signature of informed screening consent) and continues through the trial's post treatment follow-up period until the End of Trial Visit.

Any SAE assessed as related to an IMP must be reported whenever it occurs, irrespective of the time elapsed since the last administration of the IMP.

7.4.1.4 Procedure for Reporting Serious Adverse Events, Adverse Events of Special Interest and Dose Limiting Toxicities

Serious Adverse Events

In the event of any new SAE occurring during the reporting period, the Investigator must immediately (within a maximum of 24 HOURS after becoming aware of the event) inform the Sponsor or its designee and the Safety Monitoring Committee in writing.

All written reports should be transmitted using the SAE Report Form, which must be completed by the Investigator following specific completion instructions.

In exceptional circumstances, an SAE (or follow-up information) may be reported by telephone. In these cases, a written report must be sent immediately thereafter by fax or e-mail. Names, addresses, telephone and fax numbers for SAE reporting will be included in the trial specific- SAE Report Form.

Relevant pages from the CRF may be provided in parallel (e.g., medical history, concomitant medications). Additional documents may be provided by the Investigator, if available (e.g., laboratory results, hospital report, and autopsy report). In all cases, the information provided on the SAE Report Form must be consistent with the data about the event recorded in the CRF.

The Investigator must respond to any request for follow-up information (e.g., additional information, outcome, final evaluation, other records where needed) or to any question the Sponsor/designee may have on the AE within the same timelines as those noted above for initial reports. This is necessary to ensure prompt assessment of the event by the Sponsor or designee and (as applicable) to allow the Sponsor to meet strict regulatory timelines associated with expedited safety reporting obligations.

Requests for follow-up will usually be made via the responsible Monitor, although in exceptional circumstances the Global Drug Safety department may contact the Investigator directly to obtain further information or to discuss the event.

7.4.1.5 Safety Reporting to Health Authorities, Independent Ethics Committees/Institutional Review Boards and Investigators

The Sponsor will send appropriate safety notifications to Health Authorities in accordance with applicable laws and regulations.

The Investigator must comply with any applicable site-specific requirements related to the reporting of SAEs (particularly deaths) involving trial subjects to the IEC/IRB that approved the trial.

In accordance with ICH GCP, the Sponsor/designee will inform the Investigator of "findings that could adversely affect the safety of subjects, impact the conduct of the trial or alter the IEC's/IRB's approval/favourable opinion to continue the trial." In particular and in line with respective regulations, the Sponsor/designee will inform the Investigator of AEs that are both serious and unexpected and are considered to be related to the administered product ("suspected unexpected serious adverse reactions" or SUSARs). The Investigator should place copies of Safety Reports in the Investigator Site File. National regulations with regard to Safety Report notifications to Investigators will be taken into account.

When specifically required by regulations and guidelines, the Sponsor/designee will provide appropriate Safety Reports directly to the concerned lead IEC/IRB and will maintain records of these notifications. When direct reporting is not clearly defined by national or site-specific regulations, the Investigator will be responsible for promptly notifying the concerned IEC/IRB of any Safety Reports provided by the Sponsor/designee and of filing copies of all related correspondence in the Investigator Site File. All details about the country specific reporting requirements for Individual Case Safety Reports (ICSRs) and periodic safety reports to Health Authorities are described in the latest version of the Drug Safety Manual.

For trials covered by the European Directive 2001/20/EC, the Sponsor's responsibilities regarding the reporting of SAEs/SUSARs/Safety Issues will be carried out in accordance with that Directive and with the related Detailed Guidance documents.

7.4.1.6 Monitoring of Subjects with Adverse Events

AEs are recorded and assessed continuously throughout the trial (see Section 7.4.1.3) and are assessed for final outcome at the End of Trial Visit. All SAEs ongoing at the End of Trial Visit must be monitored and followed up by the Investigator until stabilization or until the outcome is known, unless the subject is documented as "lost to follow-up". Reasonable attempts to obtain this information must be made and documented. It is also the responsibility of the Investigator to ensure that any necessary additional therapeutic measures and follow-up procedures are performed.

7.4.2 Pregnancy and In Utero Drug Exposure

Not Applicable.

7.4.3 Clinical Laboratory Assessments

Stool, urine and blood samples will be collected according to the schedule given in Appendix II. The volumes of biological fluids collected at each assessment time point are presented in Appendix III. All samples should be clearly identified. Detailed description of the procedures and methods as well as the safety laboratory parameters (haematology, biochemistry and urinalysis) analysed at screening and at the End of Study visit will be given in a separate laboratory manual.

For screening diagnosis of *S. mansoni* infections urine samples will be subjected to a commercially available POC-CCA cassette test.

For diagnosis of *S. mansoni* infections, stool samples will be analysed by Kato-Katz method. Briefly, three Kato-Katz thick smears (41.7 mg) will be prepared from each stool sample (2 stools samples, 3 Kato-Katz smears per stool, i.e. total of 6 smears per subject) and read under a microscope following the instructions of the Kato-Katz manual from the World Health Organization. Infection levels will be determined as described in Section 7.1.1.

For diagnosis of *S. haematobium* co-infections, urine samples will be analysed by the filtration technique. Briefly, urine samples will be strained through filter paper and examined under the microscope for presence of *Schistosoma* eggs.

The Sponsor should receive a list of laboratory normal ranges before shipment of trial drug. Any change in laboratory normal ranges during the trial should be forwarded to Sponsor.

7.4.4 Vital Signs, Physical Examinations, and Other Assessments

7.4.4.1 Vital Signs

Vital signs including blood pressure (BP), pulse rate (PR) and body temperature will be assessed according to the trial schedule in Appendix II. Systolic blood pressure (SBP) and diastolic blood pressure (DBP) will be measured on the same arm after the subject has been in resting supine position for about 5 minutes. Pulse rate will be recorded simultaneously with the BP measurements. BP and pulse rate measurements should be obtained with the subject's arm unconstrained by clothing or other material. The measurements will be obtained with the appropriate cuff size from the opposite arm from that used for blood sampling, where possible.

Body temperature will be measured using a digital thermometer. Body temperature will be taken together with measurements of blood pressure and pulse rate.

7.4.4.2 Physical examination

Physical examination will be done according to local procedures. Body weight will be recorded during the physical examination, i.e. at screening (before dosing) and 24 hours after dosing.

7.4.4.3 Tolerability of IMP

The reaction to IMP administration (e.g., spitting, crying) will be recorded directly after dosing.

7.5 Pharmacokinetics

Not applicable

7.6 Biomarkers/Pharmacogenetics (PGx)

Not Applicable.

8 Statistics

8.1 Sample Size

Part 1: this study is exploratory. There is no hypothesis testing.

The sample size is based on the minimum number of subjects to reach a meaningful precision of the primary efficacy endpoint estimate (cure rate) in each arm, taking into account the stratification factor.

Taking into account the efficacy criteria for the selection of the dose (observed cure rate >70%), through simulations, Table 8 presents the probability of observing an overall cure rate $\ge 70\%$ based on different scenarios of true cure rates based on different strata, assuming a stratification of 40% moderate/heavy infections and 60% light infections. For example, a sample size of 50 evaluable subjects provides a probability of around 85% to observe a cure rate of $\ge 70\%$ if the overall true cure rate is 75% with 40% of moderate/heavy and 60% of light infections.

Probability of observ	Assumptions of Cure Rate in Light Infections						
cure rate \geq 70%, N=50,		70%	75%	80%	85%		
	50%	15%	27%	45%	64%		
Assumptions of Cure Rate in	55%	23%	38%	57%	76%		
Moderate/Heavy Infections	60%	33%	51%	70%	85%		
inicctions	65%	45%	63%	80%	92%		

Table 8. Probability of observing an overall cure rate ≥70% based on different scenarios of true cure rates based on different strata

Assuming an approximately 17% dropout rate, 60 subjects per arm will be randomized to ensure at least 50 evaluable subjects per arm.

Part 2: 30 subjects infected with *S. mansoni* aged 13 to 24 months (C8) and 10 subjects infected with *S. mansoni* aged 3 to 12 months (C9) will be included to evaluate tolerability and efficacy.

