Reference therapy	Rac-PZQ oral tablets (Biltricide® 600 mg) in crushed form					
	Mode of administration: the tablets (scored) will be divided into 150 mg parts, crushed, suspended in water and the solution will be swallowed after a meal.					
	Doses: 20 mg/kg t.i.d. dose given every 4 hours (cohort C1) and 40 mg/kg single dose (cohort C2)					
Planned trial and treatment duration per subject	Maximum 28 days of pre-screening and screening period, followed by 1 day treatment and 14-21 days of follow-up period.					
	Total duration per subject: up to 7 weeks.					
Statistical methods	All efficacy and safety endpoints will be analysed descriptively. Point estimation and 95% confidence interval (CI) will be calculated for primary and secondary efficacy endpoints for each treatment					

arm. The calculation of 95% CIs for proportions will rely on the Clopper-Pearson (exact) method.

The primary efficacy endpoint will be presented as cure rate (Kato-Katz method). For each treatment arm, the cure rate will correspond to the percentage of subjects becoming egg-negative 14-21 days after treatment with the study drug. Criteria for dose selection will be described in a SAP prior to first patient first dose.

Secondary endpoints will be described by treatment arms:

- Mean Egg Reduction Rate (ERR, %) 14-21 days after treatment (Kato-Katz method)
- Cure rate (POC-CCA method) as assessed by the absence of parasite antigens as determined in urine with the commercially available POC-CCA assay for *S. mansoni*

Sample size estimation

This study is exploratory. There is no null hypothesis tested.

Part 1: the sample size is based on the precision of the 95% CI of the cure rate (Kato-Katz method) in each arm. A cure rate of 70% is considered as the minimum-clinically meaningful threshold. A sample size of 50 evaluable subjects provides a probability of around 85% to observe a cure rate of \geq 70%, if the overall true cure rate is 75% (assuming 40% of moderate/heavy and 60% of light infections). Assuming an approximately 17% dropout rate, 60 subjects per arm will be randomized to ensure at least 50 evaluable subjects per arm.

Part 2: 30 subjects aged 13 to 24 months infected with *S. mansoni* (C8) and 10 subjects aged 3 to 12 months infected with *S. mansoni* (C9) will be included to evaluate drug tolerability and efficacy.

2 Sponsor, Investigators and Trial Administrative Structure

This clinical trial will be sponsored by:

Merck KGaA

[name]

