## 7 Sample Size/Randomisation

## 7.1 Sample Size

Part 1: this study is exploratory. There is no hypothesis testing.

The sample size is based on the minimum number of subjects to reach a meaningful precision of the primary efficacy endpoint estimate (cure rate) in each arm, considering the stratification factor.

There are limited historical data on the impact of the severity of infection on the observed cure rate. In the recent study by Keiser et al. (unpublished data), the observed cure rate in *S. mansoni* infected children varied between 55% and 60% in moderately infected children and 70% and 85% in light infected children depending on the dose. The table below presents the overall cure rate projections according to different assumptions of true cure rate in mild (low) and moderately infected children.

Overall cure rate (95%CI),	Assump	tions of Cure F	Rate in Light In	fections
(N=50)	70%	75%	80%	85%

	50%	62% (48%, 74%)	65% (52%, 78%)	68% (56%, 80%)	71% (60%, 82%)
Assumptions of	55%	64%	67%	70%	73%
Cure Rate in		(50%, 76%)	(54%, 80%)	(58%, 82%)	(62%, 84%)
Moderate/Heavy	60%	66%	69%	72%	75%
Infections		(52%, 78%)	(56%, 80%)	(60%, 84%)	(64%, 86%)
	65%	68% (54%, 80%)	71% (58%, 82%)	74% (62%, 86%)	77% (66%, 88%)

A minimum-clinical meaningful cure rate is considered as equal to 70%. With 50 evaluable patients enrolled, stratified as 40% moderate/heavy and 60% light, the corresponding 95% CI lower bound of an observed cure rate of 70% would be above ~58%, depending on potential difference between the strata. This sample size would also provide the minimum number of subjects to estimate the cure rate within strata.

Considering the efficacy criteria for the selection of the dose (observed cure rate >70%), through simulations, the table below presents the probability of observing an overall cure rate >= 70% based on different scenarios of true cure rates based on different strata, assuming a stratification of 40% moderate/heavy infections and 60% light infections.

Probability of observ	ring a	Assumptio	ns of Cure I	Rate in Ligh	t Infections
cure rate $\geq 70\%$ , N	=50,	70%	75%	80%	85%
	50%	15%	27%	45%	64%
Assumptions of Cure Rate in	55%	23%	38%	57%	76%
Moderate/Heavy Infections	60%	33%	51%	70%	85%
intections	65%	45%	63%	80%	92%

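### The dose-selection threshold is written as strictly above 70%, but Table 8, the 85% example and the minimum meaningful rate use or imply at least 70%, so an arm at exactly 70% has two verdicts

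*Protocol*

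**What the plan says.** Two forms of the threshold appear in the current text of both documents.

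**Strictly above 70%.** Protocol 8.1 gives the efficacy criterion in a parenthesis: "Taking into account the efficacy criteria for the selection of the dose (observed cure rate >70%), through simulations". SAP 7.1 repeats it: "Considering the efficacy criteria for the selection of the dose (observed cure rate >70%), through simulations".

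**At least 70%.** The remainder of that same sentence, in each document, tabulates the probability of an observed rate of 70% or more. The protocol caption reads "Table 8. Probability of observing an overall cure rate ≥70% based on different scenarios of true cure rates based on different strata". The worked example says that "a sample size of 50 evaluable subjects provides a probability of around 85% to observe a cure rate of" at least 70%, "if the overall true cure rate is 75% with 40% of moderate/heavy and 60% of light infections". The protocol synopsis (sample size estimation) and SAP 7.1 give the same example with the same inequality.

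**The meaning of 70%.** The protocol synopsis states: "A cure rate of 70% is considered as the minimum-clinically meaningful threshold". SAP 7.1 states: "A minimum-clinical meaningful cure rate is considered as equal to 70" per cent. If 70% is the minimum acceptable rate, a rate of 70% is acceptable.

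The protocol synopsis and section 8.6 leave the dose-selection criteria to the SAP. The SAP has no section on dose selection. The parenthesis in 7.1 is its only numerical criterion, and section 9 reports no departure from the protocol's methods.

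**The concern.** The Part 1 primary objective is to identify an ODT dose with a clinically meaningful cure rate and acceptable safety, and 70% is the only number the documents attach to the efficacy half of that choice. Up to five ODT arms (C3 to C7) are held against it. The study is open label, and the committee that recommends the dose consists of sponsor members and coordinating investigators (protocol 8.6). A pre-specified threshold should not leave that committee to settle, with results in hand, whether 70% passes.

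The second consequence concerns Table 8. It is offered as the chance of meeting the dose-selection criterion, but it is calculated for a looser event than the criterion in the sentence that introduces it. A reader who takes the criterion literally and the 85% as its probability will be too optimistic.

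**Working it through.** **Inputs**
- Evaluable children per arm: 50; randomised per arm: 60 (protocol 8.1, SAP 7.1).
- Mix: 40% moderate/heavy and 60% light, so 20 and 30 of 50, or 24 and 36 of 60.
- True cure rates in the worked example: 60% moderate/heavy and 85% light, since 0.4 × 60% + 0.6 × 85% = 24% + 51% = 75%. This is the Table 8 cell that shows 85%.

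**Counts implied by each form at N = 50**
- At least 70%: 0.70 × 50 = 35, so 35 or more cured.
- Strictly above 70%: 36 or more cured.

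**Formula.** The number cured is X = A + B, with A ~ Bin(20, p₁) for moderate/heavy and B ~ Bin(30, p₂) for light infections, independent. Then P(X ≥ k) = Σₐ P(A = a) · P(B ≥ k − a), evaluated exactly.

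**Step 1: reproduce the plan's figure.** With p₁ = 0.60 and p₂ = 0.85, P(X ≥ 35) = 84.7%, against the stated 85%. A single binomial with p = 0.75 gives 83.7%.

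**Step 2: apply the criterion as written.** P(X ≥ 36) = 75.6% (single binomial: 74.8%). The difference is P(X = 35) = 84.67% − 75.62% = 9.05 points.

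**Step 3: all of Table 8.** Each cell shows stated / 35 or more / 36 or more, in per cent.

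| Moderate/heavy | Light 70% | Light 75% | Light 80% | Light 85% |
|---|---|---|---|---|
| 50% | 15 / 14.9 / 8.8 | 27 / 27.3 / 17.9 | 45 / 44.3 / 32.0 | 64 / 63.8 / 50.7 |
| 55% | 23 / 23.0 / 14.8 | 38 / 38.5 / 27.3 | 57 / 57.1 / 44.4 | 76 / 75.4 / 63.9 |
| 60% | 33 / 33.1 / 22.9 | 51 / 50.8 / 38.5 | 70 / 69.2 / 57.2 | 85 / 84.7 / 75.6 |
| 65% | 45 / 44.7 / 33.0 | 63 / 63.0 / 50.9 | 80 / 79.6 / 69.5 | 92 / 91.4 / 85.0 |

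All 16 stated cells agree with 35 or more to within 1 point, so the table was built on at least 70%. Under 36 or more each cell falls by P(X = 35), which runs from 6.0 to 13.1 points.

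**Step 4: where the two forms differ.** An observed rate of exactly 70% needs a denominator divisible by 10. From 50 to 60 that means only 50 and 60. In between, both forms require the same count, for example 36 of 51, 39 of 55 and 41 of 58.

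**Step 5: N = 60 (24 and 36), no missing data.** With true rates of 60% and 85%, P(X ≥ 42) = 86.1% and P(X ≥ 43) = 78.4%, so exactly 42/60 has probability 7.7%. With 55% and 80%, exactly 42/60 has probability 11.6%; the corresponding probability of exactly 35/50 is 12.7%.

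**The case against.** The strongest reply is that the strict sign is a slip. It occurs once in each document, inside a parenthesis, in a sentence that goes on to use at least 70%. The caption, the worked example and the two statements of the minimum rate all point the other way. On that reading Table 8 and the 85% are right as they stand. This is persuasive as to what was probably meant. It does not remove the inconsistency, because the strict form is the one attached to the word criteria, and the SAP, which was to settle the matter, copies it.

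A reader might infer that the 85% is wrong and is really 76%. The documents do not support that. They attach 85% to observing at least 70%, and for that event it is correct. The lower figure applies only if the strict form governs.

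Three further limits stand:
- **Denominator.** Fifty evaluable children is a floor, not a forecast. The primary analysis is on the mITT set with missing outcomes counted as not cured, which keeps dropouts in the denominator. Children who need malaria treatment after dosing are removed, so one such removal from 60 makes the two forms coincide. The boundary probabilities above are conditional on N being exactly 50 or 60.
- **Use.** The protocol says "this study is exploratory. There is no hypothesis testing", and the committee weighs safety with efficacy. The threshold informs a recommendation; it is not an automatic pass or fail.
- **Unseen material.** Both documents refer to a committee charter that is not available here and may say more. The protocol nonetheless places the dose-selection criteria in the SAP.

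**Conclusion.** The concern holds as an inconsistent decision threshold. The same observed result, 35/50 or 42/60, meets the efficacy criterion on one reading of the documents and misses it on the other, and nothing in the SAP decides between them.

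In the plan's own example the choice of inequality moves the chance of meeting the criterion from 84.7% to 75.6%. This rests on exactly 50 analysed children, a fixed 20/30 split, independent outcomes and the plan's assumed stratum rates. There is no effect at denominators of 51 to 59.

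It would be tempting to conclude that the trial is smaller than it should be. That does not follow. The documents justify 50 evaluable and 60 randomised per arm by the precision of the cure-rate estimate, not by a target probability of passing 70%, so the sample size is unaffected.

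**What to change.** State one inequality for the dose-selection criterion, identically in protocol 8.1 and SAP 7.1.

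- **If at least 70% is intended:** change the sign in the parenthesis in both documents. This agrees with the caption, the worked example and the stated minimum rate, and Table 8 and the 85% stay as they are. The cost is one character in two sentences.
- **If strictly above 70% is intended:** recompute the table in both documents for 36/50 or more (the third figure in each cell above), change its heading and caption, and replace around 85% by around 76% in the protocol synopsis, protocol 8.1 and SAP 7.1. The statements that 70% is the minimum meaningful rate should then be reworded so that they do not imply that 70% qualifies. The cost is a recomputed table and a less favourable headline figure.

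Neither route changes the design, conduct or sample size. The choice should be recorded before the Part 1 results are reviewed, or, if that review has already taken place, the clinical study report should say which form was applied.
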